FGR3	fibroblast growth factor receptor 3
FMS	Feline McDonough Sarcoma
GCP	Good Clinical Practice
G-CSF	granulocyte colony-stimulating factor
GFR	Glomerular filtration rate
GI	gastrointestinal
GM-CSF	granulocyte-macrophage colony-stimulating factor
HR	hazard ratio
IC ₅₀	half maximal inhibitory concentration
ICF	informed consent form
ICH	International Council for Harmonisation
IEC	Independent Ethics Committee
IND	Investigational New Drug
IRB	Institutional Review Board
ITT	intent-to-treat
IV	intravenous

Abbreviation	Term/Definition
K-M	Kaplan-Meier
KMT2C	lysine methyltransferase 2C
KMT2D	lysine-specific methyltransferase 2D
KMT6A	lysine N-methyltransferase 6A
LLOQ	lower limit of quantification
LVEF	left ventricular ejection fraction
MedDRA	Medical Dictionary for Regulatory Activities
MEK	mitogen activated protein kinase kinase
MRI	magnetic resonance imaging
MTD	maximum tolerated dose
MUGA	multiple gated acquisition
NCCN	National Comprehensive Cancer Network
nM	nanomolar
NUx	Nephroureterectomy
N0	No cancer in nearby lymph nodes
OC	operating characteristics
ORR	overall response rate
OS	overall survival
OTC	over the counter
PD	progressive disease
PET	positron emission tomography
PFS	progression-free survival
PHI	protected health information
PIK3CA	phosphatidylinositol-4,5-bisphosphate 3-kinase catalytic subunit alpha
PK	pharmacokinetics
PR	partial response
QD	once a day
QOL	quality of life
QTcF	QTc corrected by Fridericia's formula
R _{acc}	accumulation ratio calculated as C _{min steady-state} /C _{min}
RBC	red blood cell
REB	Research Ethics Board
RECIST	Response Evaluation Criteria in Solid Tumors

Abbreviation	Term/Definition
RFS	recurrence-free survival
RNA	ribonucleic acid
RNAseq	Ribonucleic acid sequencing
RPTD	recommended phase 2 dose
SAE	serious adverse event
SAP	Statistical Analysis Plan
SD	stable disease
TACE	transarterial chemoembolization
TCGA	The Cancer Genome Atlas
TdP	Torsades de Pointes
t _{max}	time at which the maximum observed concentration (C _{max}) occurs
TMP/SMX DS	trimethoprim and sulfamethoxazole
TP53	tumor protein p53
UCC	urothelial cell carcinoma
ULN	upper limit of normal
UNK	unknown
URS	Ureteroscopy
UTMDACC	University of Texas MD Anderson Cancer Center
UTUC	Upper tract urothelial carcinoma
Ux	Ureterectomy
WBC	white blood cell
WOCBP	woman of childbearing potential
ypT0	complete pathologic response after treatment
ypT1	pathologic superficial invasion after treatment

1. SCHEDULE OF ASSESSMENTS

VISIT/CYCLE	SCREENING PHASE ^a	TREATMENT PHASE				FOLLOW UP PHASE	
		CYCLE #1	CYCLE #2	PRE-OP/ SAFETY VISIT	SURGERY	POST-OP FOLLOW-UP	1-YEAR FOLLOW-UP
Scheduling window (days)	-28 to -1	1	29(± 7)	57 (± 14)		30 post-op (± 14)	365 post-op (± 30)
Informed Consent	X						
Eligibility Criteria	X						
Medical History	X						X
Physical Examination	X	X		X			X
Vital Signs	X	X	X	X		X	X
URS/Tumor Mapping	X				X		X ^b
Nephroureterectomy					X		
Surgical Specimen Assessment/Tumor Mapping		X			X		
Ophthalmic Assessment	X		X			X ^d	
Safety Laboratories ^c	X	X	X	X		X	X
Urinalysis	X	X	X	X		X	
Pregnancy Test	X	X	X	X		X	
12-lead ECG	X			X			
Echocardiogram	X						
AE Assessment	X	X	X	X		X	
Concomitant Meds	X	X	X	X	X	X	
EORTC QLQ-C30 QOL Questionnaire		X		X		X	
Drug Dispensing		X	X				
Drug Accountability			X				
Blood for Correlatives	X			X		X	
Urine for Correlatives	X			X		X	
Tissue for Correlatives	X				X		

Abbreviations

- a. Baseline/screening assessments that are conducted within 3 days prior to first treatment can be used to satisfy the Day 1 requirements. Every effort must be made to follow the schedule outlined.
- b. CT scan and cystoscopy (+/-URS)
- c. Blood draw (phosphate level testing only) on Day 14 (+/-7 days)
- d. as per physician discretion

2. BACKGROUND

Upper tract urothelial carcinoma (UTUC) is typically considered similar as bladder urothelial cancer just occurring upstream in the ureter or renal pelvis, but there are unique molecular and clinical aspects that differentiate it from its more common counterpart. Unique aspects of UTUC include causation by exposure to aristolochic acid (found in many eastern herbal remedies and accounting for the high rates in the East), high rates of microsatellite instability, strong predisposition in those with Lynch syndrome, and high rates of FGFR3 mutations.

Generally, treatments are allocated based on biopsy showing low grade versus high grade disease. Treatments for those with low-grade disease include endoscopic management only, which allows preservation of kidney function but is associated with multiple procedures and high rates of recurrence. Endoscopic treatment of UTUC is often imperatively needed to avoid placing older patients on dialysis, or in those with low-grade, low-volume disease who wish to retain their kidney and avoid major surgery. Limitations of endoscopic management include the need to perform multiple procedures in staged fashion, an inability to manage large volume disease, and a 30-80% recurrence rate. No standard adjuvant therapy exists in this population although many, including us, have tried topical therapies with variable success rates of 40-70% RFS. The standard accepted treatment however is surgery with nephroureterectomy or ureterectomy (NUx/Ux), which creates or worsens existing renal insufficiency in many cases, and is associated with high complication rates given the typically elderly population. Ureteroscopic (URS) management is an option that can preserve the kidney but is associated with significant recurrence rates.

Patients with high-grade disease are preferentially treated with neoadjuvant chemotherapy followed by NUX/Ux with lymph node dissection, or initial NUX/Ux followed by adjuvant chemotherapy. Reductions in kidney function limit the effective delivery of adjuvant therapy. Based on our seminal work showing significant downstaging and improved survival, the first intergroup prospective trial for this disease showed that the majority of patients had downstaging to ypT1 or less with a 14% ypT0N0 rate (Censits-Hoffman J et al, AUA 2018). As one of the highest recruitment sites for this trial, however, we noted a 50 -70% screen failure rate for this population, rendering a significant portion of patients ineligible. Thus, for both low and high risk patients, there are still major unmet needs.

Recent genomic studies indicate a high rate of FGFR3 mutations in patients with UTUC. We reported an integrated, comprehensive genomic study on UTUC, using whole exome sequencing, RNAseq, and protein expression. These data confirm that the most common mutation in UTUC occurs in FGFR3 (74.1% prevalence for the entire cohort of 31 patients). Low-grade UTUC tumors were associated with a 92% rate of FGFR3 mutations, and, more interestingly, high-grade with a 60% rate of FGFR3 mutations, much higher than is seen in bladder cancer (19% in TCGA bladder cohort, if all somatic mutations, fusions, and amplifications are counted), and largely consistent with another UTUC genomic study from Memorial Sloan Kettering. Other mutations in order of decreasing frequency were KMT2D, PIK3CA, TP53, KMT2C, and KMT6A. Mutations of other FGFR subtypes were identified at a much low rate. Expression profiling revealed 4 subtypes that do not exactly match the subtypes described for bladder cancer, with 2 of the 4 subtypes having 100% rate of FGFR3 mutations but with varying clinical correlates between these 2 subtypes.

The emerging data from infigratinib, an inhibitor of FGFR1-3, showed a well-tolerated drug with activity against tumors with FGFR alterations. This represents a unique opportunity to study the tolerability of this compound in those without metastatic disease but who have a great need for therapeutic options, and also provides an opportunity to study the inhibition of FGFR-related pathways in UTUC. In a recently published study (Pal S et al, Cancer Discovery 2018) in patients with incurable urothelial cancer, the most common adverse events were asymptomatic, reversible laboratory derangements: hyperphosphatemia (46%), elevated creatinine (42%), fatigue (37%), constipation (37%), anemia (36%) and decreased appetite (33%). The most common grade 3/4 AEs were hyperlipidemia (10%), and fatigue, hypophosphatemia, and palmar-plantar erythrodysesthesia each at 7%. The current proposal involves patients with localized and locally advanced disease, who may have a different tolerability profile as well as different motivations to pursue novel therapeutic options.

Given its relatively low serious adverse event profile, the high rates of FGFR3 mutations in UTUC, and the major unmet needs for this disease, sufficient rationale exists to further study its activity in UTUC. We propose a study in patients with localized/locally advanced UTUC in order to further understand tolerability and biologic consequences of FGFR inhibition with a biomarker-informed neoadjuvant study, which could help inform a future phase 2 efficacy study in this population.

2.1. Overview of Disease Pathogenesis, Epidemiology and Current Treatment

2.2. Overview of Infigratinib

Infigratinib is an orally bioavailable, potent and selective inhibitor of FGFRs 1-3, which has demonstrated anti-tumor activity in preclinical *in vitro* and *in vivo* tumor models harboring FGFR genetic alterations (data on file). Infigratinib belongs to the pyrimidinyl aryl urea chemical class and its chemical name is 3-(2,6-Dichloro-3,5- dimethoxyphenyl)-1-{6-[4-(4-ethyl-1-piperazin-1-yl)phenylamino]-pyrimidinyl-4-yl}-1methylurea phosphate(1:1).

Please refer to the Investigator's Brochure for additional information on infigratinib.

2.3. Preclinical Experience with Infigratinib

At the cellular level, infigratinib selectively inhibits the kinase activity of FGFR1, FGFR2 and FGFR3, as measured by inhibition of receptor autophosphorylation, with half maximal inhibitory concentration (IC₅₀) values of 3 to 7 nM for FGFR1, FGFR2 and FGFR3.

Infigratinib is less selective for FGFR4, with an IC₅₀ of 168 nM. In cellular kinase selectivity assays, the most potently inhibited kinases, in addition to the FGFRs, were vascular endothelial growth factor receptor 2 and FMS-related tyrosine kinase 1, with IC₅₀ values of 1510 nM and 1591 nM, respectively (data on file).

Consistent with inhibition of FGFR autophosphorylation, infigratinib inhibits FGFR downstream signaling and proliferation of human cancer cell lines harboring genetic alterations of the FGFRs. These include, among others, lung and breast cancer cell lines with FGFR1 gene amplification, gastric cancer with FGFR2 gene amplification, endometrial cancer with FGFR2 mutations and bladder cancer with FGFR3 mutations or FGFR3 translocations ([Wesche et al., 2011](#); [Guagnano et al., 2012](#); [Konecny et al., 2013](#)).

In vivo, infigratinib is widely distributed to tissues in the rat. A battery of *in vivo* safety pharmacology studies in rats and dogs did not reveal any effects on central nervous or respiratory systems and on hemodynamic or electrocardiographic parameters, respectively.

In repeated dose (oral gavage; up to 4-weeks) toxicity studies, infigratinib did lead to increases in serum fibroblast growth factor 23 and serum phosphorous associated with partially reversible ectopic mineralization (kidney, lung, vascular and digestive systems) along with largely reversible changes in renal function parameters and bone growth plate thickening / retention of the primary spongiosa in rats (≥ 10 mg/kg/day) and dogs (≥ 10 mg/kg/day). These effects were deemed to be on-target effects mediated by pharmacological inhibition of FGFR.

The no observed adverse effect level in the dog and rat was 1 mg/kg.

2.4. Clinical Experience with Infigratinib

2.4.1. Clinical Pharmacokinetics and Phase 1 Data

The pharmacokinetics (PK) of infigratinib and its active metabolites have been evaluated following single and repeat daily doses in a phase 1 study (CBGJ398X2101).

Following a single dose, median T_{max} was approximately 2-3 hours. Infigratinib had a relatively short median elimination half-life ranging from 2.69 to 5.71 hours on Day 1. Despite the relatively short half-life on Day 1, accumulation was observed with daily dosing at doses ≥ 60 mg, likely due to auto-inhibition of CYP3A4 mediated clearance pathways (data on file). Mean accumulation ratio (R_{acc}) ranged from 3 to 8 on Days 15 and 28. The interpatient variability was high for infigratinib.

In the single agent, first-in-human phase 1 study (CBGJ398X2101), infigratinib was evaluated at 9 different dose levels and 3 different dose schedules, ranging from 5 mg/day to 150 mg/day. Eight dose levels were administered on the once daily continuous 28-day cycle schedule, and one dose level was administered on a twice a day continuous 28-day cycle schedule. One subject at 100 mg experienced Grade 3 alanine aminotransferase (ALT) and aspartate aminotransferase (AST) elevation, 1 subject at 125 mg daily experienced hyperphosphatemia, and 2 subjects at 150 mg experienced Grade 1 corneal toxicity (1 subject) and Grade 3 ALT and AST elevation (1 subject). The dose of infigratinib 125 mg once daily continuously was declared as the maximum tolerated dose (MTD).

While dose levels of 100 mg QD and higher were tolerated by subjects, the majority of subjects experienced reversible hyperphosphatemia, which led to study drug interruptions (data on file). An evaluation of the drug administration records for subjects prior to receiving prophylactic phosphate-lowering therapy indicated that the median time until first dose interruption was approximately 22 days and the median duration of interruption was 7 days. This observation led to the introduction of an expansion arm to evaluate the administration of 125 mg QD on a 3 week on (21 days) / 1 week off (7 days) schedule in 28-day cycles. Subjects treated with this alternative dosing schedule required less dose interruption ($n=24$, 49.0%) compared with subjects treated with 125 mg continuously ($n=40$, 70.2%). Thus, infigratinib 125 mg once daily on a 3 weeks on/1 week off schedule was declared as the recommended phase 2 dose (RPTD).

In the dose escalation cohort of 92 subjects, no complete response (CR) was observed, and 4 subjects had partial response (PR) (1 subject at 100 mg; 3 subjects at 125 mg continuous dose).

Of the 173 subjects treated at the 125 mg continuous or intermittent schedule, CR was observed in 2 subjects (1.2%), and 22 subjects (12.7%) had PR. The ORR (95% confidence interval [CI]) and disease control rate (95% CI) were 13.9% (9.10, 19.94) and 49.1% (41.47, 56.83), respectively.

The median PFS for all subjects treated at the MTD/RPTD was 3.12 months (95% CI: 2.10, 3.65 months).

Please refer to Investigator's Brochure for more details regarding phase 1 studies and pharmacokinetics.

2.4.2. Clinical Safety

The majority of Study BGJ398X2101 patients (99.0%) evaluable for safety experienced at least one AE, with a Grade 3/4 AE reported in 58.7%, regardless of study treatment relationship. The incidence of Grade 3/4 AEs was similar at the MTD (52.6%). The majority of these patients (95.7%) experienced at least 1 AE suspected to be study treatment related, with Grade 3/4 AEs suspected to be study treatment related reported in 38.0%. The incidence of Grade 3/4 AEs suspected to be study treatment related (38.0%) was similar at the MTD (31.6%).

The most common AEs (occurring in $\geq 30\%$ of all patients, all grades), regardless of study treatment relationship were: hyperphosphataemia (65.4%), constipation (39.9%), decreased appetite (37.5%), fatigue (36.1%), stomatitis (34.1%), and nausea (32.2%). The most common AEs suspected to be study treatment related (occurring in $\geq 30\%$ of all patients, all grades) were: hyperphosphatemia (63.5%) and stomatitis (33.7%).

The most commonly reported Grade 3/4 AEs (in $\geq 4\%$ of all patients), regardless of study treatment relationship were: hyperlipasaemia (6.7%), hypophosphatemia (6.3%), ALT elevation (5.3%), hyperphosphatemia (4.8%), and fatigue (4.8%). The most frequently occurring Grade 3/4 AEs suspected to be study treatment related (in $\geq 4\%$ of all patients) were: hyperlipasaemia (5.8%), hyperphosphatemia (4.8%), and ALT increased (4.8%).

A total of 57 deaths (27.4%) occurred during the study, and most of these deaths were due to disease progression (24.0%). Of the total deaths, 11.1% were on-treatment deaths; of these, 8.6% patients died due to disease progression, 2 patients died due to sepsis, and 1 patient each died due to respiratory failure, cardiac arrest, and unknown reason.

At least one SAE (occurring in $\geq 5\%$ patients) of any grade, regardless of study treatment relationship, was reported in a total of 37.5%, with a similar incidence reported at the MTD (40.4%). SAEs suspected to be drug-related were reported in 8.6% of patients. The most commonly reported SAEs, by preferred term (occurring in $\geq 5\%$ patients) were: general physical health deterioration (2.9%); pneumonia (2.9%); vomiting (2.9%); dyspnoea (2.4%); and, hypercalcaemia (2.4%).

Adverse events leading to study drug discontinuation were reported in a total of 14.4%. Most commonly reported AEs leading to discontinuation of study drug, in all patients, by preferred term were: visual impairment, hypercalcemia, hypercreatininaemia, hyperlipesaemia, and palmar-plantar erythrodysaesthesia syndrome in 1.0% each. Twenty-one patients (10.1%) discontinued treatment due to AEs that were suspected to be related to study treatment. The common suspected AEs leading to study treatment discontinuation were: visual impairment, hypercalcemia, hypercreatininaemia, hyperlipasaemia, and palmar-plantar erythrodysaesthesia syndrome in 1.0% each.

AEs requiring dose interruption or reduction occurred in 68.3% of patients. The most common AEs (incidence $\geq 10\%$) requiring dose adjustment or temporary interruptions regardless of study drug relationship were hyperphosphatemia (28.8%) and hypercreatininaemia (15.9%).

Overall, Grade 3 hematology abnormalities were reported in 13.9%, of which, two SAEs of anemia were reported in 2 patients (one patient had Grade 2 anemia and the other had Grade 3 anemia). New or worsened Grade 4 hematology abnormality of lymphocytes decrease was reported in 1.5% of patients.

Eye-related AEs were reported in a total of 44.7% of patients. Of these, AEs suspected to be study treatment related were reported in 33.7%. There was one Grade 2 SAE of keratitis reported which was suspected to be treatment related and led to study drug discontinuation ([BGJ398X2101 Clinical Study Report; Pal et al 2018](#)).

Please refer to the Infigratinib Investigator Brochure for additional safety information.

2.4.3. Clinical Efficacy

Efficacy data for all patients in the dose escalation and dose expansion parts of Study BGJ398X2101 are available in the Investigators Brochure. The following efficacy data presented are for study expansion part patients with UCC.

Arm 4 of the expansion part of Study BGJ398X2101 included 67 patients with advanced/metastatic UCC with FGFR3 mutations or FGFR gene fusions who had either progressed on or were intolerant of platinum-based chemotherapy, or had contraindications to platinum-based chemotherapy. Permitted FGFR3 mutations included mutations in exon 7 (R248C, S249C), exon 10 (G372C, A393E, Y375C), or exon 15 (K652M/T, K652E/Q). Permitted FGFR3 gene fusions included, but were not limited to the FGFR3-TACC3 fusion. Patients were treated with oral BGJ398 125 mg/day for 21 days followed by 7 days without treatment as 28-day cycles.

All 67 patients were evaluable for response. Seventeen patients (25.4%) had responses (1 CR and 16 PR). Forty-three patients (64.2%) had disease control (CR + PR + SD). Sixteen patients (23.9%) had progressive disease and eight patients (11.9%) had an indeterminate response. One patient with an indeterminate response by Response Evaluation Criteria in Solid Tumors (RECIST) criteria actually had a pathologic complete response; however, due to changing imaging modalities between assessments, the response was reported as unknown. The patient had primary bladder cancer and a histologically confirmed metastasis in the humerus. During BGJ398 treatment, the patient had surgical resection of a suspected

pathologic fracture of the humerus. Histologic assessment revealed no evidence of residual disease ([BGJ398X2101 Clinical Study Report; Pal et al 2018](#)).

Please refer to the Infigratinib Investigator Brochure for additional efficacy information.

2.5. Rationale

2.5.1. Study Rationale and Purpose

Given the relatively low serious adverse event profile of Infigratinib, the high rates of FGFR3 mutations in UTUC, and the major unmet needs for this disease, sufficient rationale exists to further study its activity in UTUC. We propose a study in patients with localized/locally advanced UTUC in order to further understand the tolerability and biologic consequences of FGFR inhibition with a biomarker-informed neoadjuvant study, which will help inform a future phase 2 efficacy study, as well as a phase 3 adjuvant study in this population.

2.5.2. Rationale for the Study Design

This neoadjuvant, window of opportunity trial will allow the evaluation of tolerability by a drug previously exposed only to metastatic patients. In the process, we also have an opportunity to study response rates of UTUC and immunologic consequences of FGFR3 inhibition. Arguments supporting this trial are: 1) A strong scientific rationale with an obligation to study this drug given the very high rates of FGFR3 alterations in this population, 2) an unmet clinical need, and 3) supportive Phase 1 data.

2.5.3. Rationale for Dose and Regimen Selection

In this study, subjects will receive 125 mg QD of infigratinib on a 3 week on (21 day) /1 week off (7 day) schedule in 28-day cycles, for a total of 2 cycles. This dose level and regimen is based on experiences from previous phase 1 and 2 trials.

OBJECTIVES AND ENDPOINTS

2.6. Objectives

The **primary objective** is to evaluate the tolerability of infigratinib in patients with low-grade and high-grade platinum ineligible UTUC.

The **secondary objectives** are to:

- Assess tolerability in those with GFR 30-49
- Evaluate the objective response rate (CR+PR) of infigratinib after 2 cycles in UTUC with and without FGFR3 alterations
- Correlate tumor tissue FGFR3 alteration (presence/absence, alteration type, and clonal status) with response and occurrence/severity of AEs such as hyperphosphatemia

- Evaluate, bladder and local/distant recurrence within 12 months in those undergoing NUX/Ux and upper tract, bladder, and local/distant recurrence within 12 months in those undergoing endoscopic management.
- Evaluate renal function pre-treatment and after two treatments.
- Evaluate patient-reported quality of life (QOL) outcomes during treatment.

The **exploratory objectives** are to:

- Explore intra-tumor heterogeneity, gene expression profiles, and changes in tumor microenvironment using single cell RNA sequencing (scRNA-seq) and CyTOF pre and post treatment to identify potential mechanisms of response and/or resistance, and correlation with the occurrence/severity of AEs.
- Explore urinary/upper tract washing FGFR3 alterations as potential biomarker for detection and response
- Explore cfDNA for detection of FGFR3 alterations and as a predictor of response

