2.7. Endpoints

The primary endpoint is the proportion of patients who are not able to complete treatment due to excessive toxicity. Toxicity will be tabulated by type, frequency, and severity of AEs and serious AEs (SAEs), laboratory abnormalities, and other safety findings.

The secondary endpoints are:

- Percentage of patients achieving a point in time objective response (either complete or partial response [CR or PR]) after 2 cycles of infigratinib. Tumor mapping will be performed from the endoscopic evaluation (after any biopsies) and this will be used to compare to pathologic (NUX/Ux cohort) or ureteroscopic (endoscopy cohort) findings in order to determine responses.
- Tumor mapping will be performed based on endoscopic findings, noting location, number of tumors, tumor architecture, and location of biopsies; and will again be performed during pathologic evaluation again noting size, location, number of tumors, architecture, and absence of tumor at any previously identified tumor. A difference of 3mm will be considered within error of measurement.
- Mutational analysis will be performed on FFPE tumor tissue using a comprehensive mutation panel (T200.2) which we have used in prior studies and includes all previously identified UTUC mutations, including all relevant FGFR3 alterations including hot spots, copy number variations and fusions. Blood collected at baseline will be used as germline source.
- All analyses will be performed on patients stratified as having or not having FGFR3 alterations. Descriptive statistics will be used to summarize various clinical parameters.
- The same methods will also be used to explore the association of AEs such as hyperphosphatemia with response.
- Percentage of patients with no evidence of disease 12 months after surgery

- Changes in patient reported QOL outcomes will be measured using a validated questionnaire (EORTC QLQ-C30 v3), administered at 3 time points: 1. enrollment (after enrollment and before first dose), 2. after completion of 2 cycles and prior to surgery, and 3. at 1 month postoperative check.

The exploratory endpoints are:

Tumor Studies:

- Single cell (sc)RNAseq will be performed on fresh frozen tumors using 10x Genomics platform. Tumor cell heterogeneity, FGFR3 gene expression, and tumor microenvironment will be profiled. All bioinformatics data analysis will be performed in the MD Anderson Genomics core as part of the Rare Tumor Initiative Program (2014-0938)

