5. TREATMENTS

5.1. Treatments Administered

Patients will receive infigratinib 125 mg orally every day for a total of 2 cycles. Each cycle will consist in 28 days, with a schedule of 3 weeks on, 1 week off. Surgery will be performed during weeks 8-9 (week 8 being the off-week of 2nd cycle), and patients will have taken last dose of Infigratinib at least 48 hours prior to surgery.

If patients are not able to tolerate the study drug, every effort will be made to schedule the surgery as soon as possible after the patient has recovered and/or the investigator determines it is the best course of action for the patient.

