7.5. Pre-op Visit

All patients will be required to return to clinic for pre-operative assessment within 14 days prior to the surgical procedure. Assessments will include the following:

- Weight
- Concomitant medication use
- Physical examination
- Vital signs
- Blood draw for hematology, chemistry
- Collection of blood and urine for correlative studies
- Pregnancy test (blood or urine) for WOCBP
- 12-lead ECG
- AEs
- EORTC QLQ-C30 QOL Questionnaire

NOTE: Collection of tissue for correlative studies **at surgery**

7.6. 30-day Safety Follow-up Visit

All subjects must complete safety follow-up assessments 30 days (+/- 14 days) after the last dose of the study drug or surgery, whichever occurs last. Information relating to anticancer therapies taken since discontinuation of study drug and AEs (including concomitant medication taken for ongoing AEs) will be collected for 30 days after the last dose of the study drug. Assessments will include the following:

- Vital signs
- Ophthalmic assessment (per treating physician's discretion)
- Blood draw for hematology, chemistry
- Urinalysis (macro, micro only if necessary)
- Collection of blood and urine for correlative studies
- Pregnancy test (blood or urine) for WOCBP
- EORTC QLQ-C30 QOL Questionnaire

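### Quality of life during treatment is a secondary objective, but no questionnaire is planned on a dosing day, and the timing of the pre-operative one differs between sections

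*Combined protocol and SAP*

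**What the plan says.** All references are to the combined protocol and SAP.

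- **Objective (Section 2.6):** "Evaluate patient-reported quality of life (QOL) outcomes during treatment".
- **Endpoint (Section 2.7):** change in QLQ-C30 scores over three administrations. The first is before any dose; the other two are "after completion of 2 cycles and prior to surgery, and 3. at 1 month postoperative check".
- **Schedule of Assessments (Section 1):** the row "EORTC QLQ-C30 QOL Questionnaire" is marked at Cycle 1 (Day 1), the pre-operative visit (Day 57 ± 14) and the post-operative visit (30 days ± 14). The Cycle 2 column (Day 29 ± 7) is blank.
- **Visit lists (Sections 7.2 to 7.6):** the pre-operative and 30-day lists include the questionnaire. The baseline one appears under screening, not Day 1, but is still before dosing. Section 7.4, on the rest of the treatment period, lists none.
- **Dosing (Section 2.5.3):** "3 week on (21 day) /1 week off (7 day) schedule in 28-day cycles, for a total of 2 cycles".
- **Surgery (Section 5.1):** weeks 8-9, with week 8 named as the off-week of cycle 2.
- **Pre-operative visit (Section 7.5):** "within 14 days prior to the surgical procedure".
- **Analysis (Section 9):** paired tests between two time points and linear mixed models over time. The section expects its analyses to be largely descriptive at this sample size.

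**The concern.** An objective about quality of life during treatment would normally have at least one measurement while the patient is taking the drug. Here the drug is given in two three-week blocks, and the questionnaires appear to sit before the first block, after the off-week that follows the second, and after surgery. If so, no planned contrast describes the on-drug state, and neither a paired test nor a mixed model can recover a state that was not observed.

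This matters more than usual because little else in the trial records lower-grade symptoms. Section 8.2.1.3 captures adverse events only if they are Grade 3 or higher and drug-related. In the phase 1 data in Section 2.4.2, fatigue was 36.1% at all grades but 4.8% at Grade 3/4. Constipation (39.9%), decreased appetite (37.5%), stomatitis (34.1%) and nausea (32.2%) were common, yet none is among the Grade 3/4 events listed there at 4% or more. The QLQ-C30 is the only patient-reported measure planned.

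**Working it through.** **Inputs.** Cycle length 28 days, 21 on and 7 off, two cycles (Section 2.5.3). Pre-operative visit Day 57 ± 14, Cycle 2 visit Day 29 ± 7, post-operative visit 30 ± 14 days (Section 1). Surgery in weeks 8-9 (Section 5.1), that is Days 50-63.

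**Step 1: dosing days.** Cycle 1 is Days 1-21. Cycle 2 is Days 29 to 28 + 21 = 49. Total: 2 × 21 = 42 dosing days.

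**Step 2: the plan's own visit day.** The first day after two full cycles is 2 × 28 + 1 = Day 57, which matches the schedule.

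**Step 3: nominal questionnaire dates against dosing.**

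| Questionnaire | Nominal day | Relation to drug |
|---|---|---|
| Baseline | screening or Day 1, before dosing | not yet on drug |
| Pre-operative | Day 57 | 57 − 49 = 8 days after last scheduled dose |
| Post-operative | 50 + 30 = 80 to 63 + 30 = 93 | 80 − 49 = 31 to 93 − 49 = 44 days after last dose |

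None of the three falls on a dosing day.

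**Step 4: the second questionnaire under each section.**

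- *Section 2.7* requires it "after completion of 2 cycles and prior to surgery". With nominal cycles, that is Day 57 or later. If surgery is by Day 63, the gap from last dose is 57 − 49 = 8 to at most 63 − 49 = 14 days.
- *Section 1* allows 57 − 14 = Day 43 to 57 + 14 = Day 71. Days 43-49 are dosing days: 7 of the 29 days in the window.
- *Section 5.1* allows surgery in week 8 (Days 50-56). Two full cycles end on Day 2 × 28 = 56, so a patient operated on in that week cannot have a questionnaire that is both before surgery and on Day 57 or later.
- *Section 7.5* allows the visit up to 14 days before surgery. For week-8 surgery that reaches back to Days 36-42, so Days 43-49, which the Section 1 window also allows, are permitted.

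**Step 5: shift in the start of cycle 2.** A start on Day 22, 29 or 36 gives a last dose on Day 42, 49 or 56. A Day 57 visit is then 15, 8 or 1 days after it. Two completed cycles always put the questionnaire at least 8 days after the last scheduled dose, but for a Day 36 start that is Day 64, beyond the planned surgery period.

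**Step 6: an existing on-drug contact.** Footnote c of the schedule has a phosphate blood draw on Day 14 ± 7, that is Days 7-21. All of these are cycle 1 dosing days.

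**The case against.** The strongest reply is that the objective is worded loosely and the endpoint is clear. The schedule places the pre-operative visit under its treatment-phase heading, and Section 2.7 spells out changes across three named time points. In a neoadjuvant trial, the condition in which patients reach surgery is a legitimate target. This stands as far as it goes: the planned contrasts are meaningful, and rewording the objective would remove the mismatch. It does not supply an on-drug measurement.

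Three stronger readings are tempting and are not supported.

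- A reader might infer from the Day 43-71 window that the plan intends a mixture running from on drug to 71 − 49 = 22 days off drug. Section 2.7 excludes Days 43-49, and Day 71 lies beyond planned surgery (Day 63), so it is reached only if surgery is late. What remains is a lack of alignment between sections, which could let some questionnaires be completed early.
- A reader might infer that the analyses will mainly describe recovery after stopping drug. Without an on-drug score, nothing in the plan measures recovery. The first contrast is net change from baseline to after treatment.
- A reader might infer that drug-related loss of quality of life will be missed. That depends on how quickly such effects ease, which the documents do not say.

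It is also fair to say that the Day 14 draw is for phosphate alone and that Section 7.4 allows local laboratories, so an added questionnaire may need remote completion.

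**Conclusion.** The mismatch is real. At nominal dates 0 of 3 questionnaires fall within the 42 dosing days, and the nearest comes 8 days after the last scheduled dose (8-14 days if two cycles are completed and surgery is by Day 63). The trial can report net change after treatment and after surgery, but not quality of life while taking drug. That it may miss effects easing in the off-week is plausible but rests on an assumption about speed of resolution.

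Separately, Sections 1, 2.7, 5.1 and 7.5 do not agree on when the second questionnaire may be completed. Read alone, some of them allow it on drug.

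The day counts assume uninterrupted dosing on nominal dates. Interruptions or early stopping change the gap, and no questionnaire is tied to discontinuation. The questionnaire's recall period is not given in the documents and is not used here.

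The consequence is limited to a secondary, mainly descriptive endpoint in up to 20 patients. A reader might infer that the tolerability result is compromised. It is not: the primary endpoint is toxicity-related failure to complete treatment, and neither its estimate nor the stopping rule uses the questionnaire.

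**What to change.** 1. Add one QLQ-C30 during cycle 1 dosing, timed with the existing Day 14 (±7) blood draw and completed remotely where the draw is at a local laboratory. Report the change from Day 1 to this time point alongside the planned contrasts.
2. Record days since last dose at the pre-operative questionnaire, so that the drug state at completion is known for each patient.
3. Reconcile Sections 1, 2.7, 5.1 and 7.5 on when the second questionnaire is completed relative to the end of cycle 2 and to surgery.
4. If no time point is added, restate the objective as quality of life before treatment, after treatment and after surgery.

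The cost is one extra questionnaire per patient (up to 20), remote collection for some, and one added data field. The fallback in item 4 costs only a wording change.
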